Participating GP surgeries will only be informed of their patient's participation in the study following receipt of informed consent. All data storage and handling will follow the principles of good clinical practice. All human tissue samples will be labelled anonymously and stored in accordance with the Human Tissue Act (2004).

4. Objectives and Outcome Measures

Primary Objectives:

The primary aim of the research is to assess the feasibility of conducting a randomised control trial to evaluate the effectiveness of a focused 15-minute one-to-one consultation in a primary care setting with a health-care professional to improve blood glucose control in pre-diabetes.

The study aims to quantify the following:

- the number of patients with an HbA1c between 42 and 47 mmolmol⁻¹ during the recruitment phase
- the percentage of patients eligible to participate who gave consent to be part of the study
- the percentage of patients who completed baseline testing; 3 month; and 6 month testing

Secondary Objectives

Secondary research questions aim to determine the impact of the consultation on the following measures at 3 and 6 months:

HbA1c

Cholesterol

BMI

Waist and hip girth

Blood pressure

Body composition

Physical activity level

Dietary habits

5. Study Design

This feasibility study will use a randomised control design to assess the effectiveness of a 15 minute one to one consultation compared to no treatment.

6. Study Setting:

All research activity included in the baseline, 3 month and 6 month visits will be completed within the [name], Aberystwyth University. The 15 minute pre-diabetes consultations will take place within Church Surgery, Aberystwyth.

7. Participant Eligibility

Participants will be eligible for participation if they are registered with Church Surgery and have an HbA1c (recorded within the last year) of between 42 and 47 mmol⁻¹.

8. Inclusion and Exclusion Criteria

Inclusion Criteria	Exclusion Criteria
Age > 18, < 80	Under judicial control
Able to provide consent	Unable to understand and follow instructions due to cognition or language problems or provide consent
Registered with a mid-Wales GP surgery	
HbA1c between 42 mmol·mol ⁻¹ and 47 mmol·mol ⁻¹	

9. Participant Identification and Recruitment

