Upon completion of this phase of data collection, participants will be provided with a series of validated questionnaires to complete (to be completed at every visit unless otherwise stated). These include; the International Physical Activity Questionnaire- Short Form (IPAQ-SF), Food Frequency Questionnaire (FFQ; EPIC-Norfolk; baseline and 6 months), SF-36 (36-Item Short Form Survey Instrument) and components of the Personal Diabetes Questionnaire (baseline). Participants will complete the questionnaires unassisted although members of the research team will be available to answer any questions the participant may have relating to the questionnaires. Lastly, participants will receive instructions on the use of the urine collection kit for dietary monitoring (see below) and the ActiGraph for physical activity monitoring (if randomised; see below). Participants will then be free to leave the laboratory. An additional acceptability questionnaire designed by the research team will be given to participants at the end of the 6 month visit and will include questions relating to the WARU visits, 15 minute consultation (if received), urine collection and ActiGraph use. Visits will last between approximately 120 minutes and 150 minutes depending on the time taken for participants to complete the relevant questionnaires.

Following completion of the baseline visit, participants will be randomised into either the intervention group (INT) or the control group (CON). Randomisation will be achieved using a minimisation software package (Minim) and will ensure that there will be only minor differences between groups in the variables used in the allocation process. Participants in INT will receive a focussed 15 minute one to one consultation with a practice nurse at their registered general practice. The consultation derives from the original 30 minute protocol employed during a previous study conducted by the present research team (Thatcher and Gregory, 2017) which used 104 GP-registered patients. The first half of the 30 minute consultation in that study (led by general practise) collected baseline data (height, weight, waist circumference, blood pressure)

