Participants can choose any day within the week to begin wearing the ActiGraph but must then wear it for the following 7 days unless unfeasible to do so (e.g. swimming, bathing or showering). In this instance, participants will record at what time and the amount of time they are not wearing the ActiGraph. Should participants forget to wear the device; the same procedure will be followed. Should participants miss a whole day; they must record for an extra day directly after the 7th day. An additional sheet will be provided for participants to record any time when the device is not worn. Participants do not need to wear the ActiGraph when sleeping although they must record the time they go to sleep and at what time they wake up. Participants must fit the ActiGraph in the morning as soon as it is feasible to do so. Participants can return the ActiGraph at the end of the 7 day recording period either in person or by post.

14. Randomisation Procedure

Randomisation will be achieved using a minimisation software package (Minim) and will ensure that there will be only minor differences between groups in the variables used in the allocation process. Participant details will be recorded after the first visit and inputted into the randomisation package. Following randomisation of the first participant, remaining participants will be randomly allocated into either the intervention or control based upon age (ages 60+ in both groups / equal distribution of sex and BMI 30 kg/m² + in both groups). Randomisation will be conducted primarily by the academic supervisor. Church surgery will be informed of the patients who have been randomised to receive the intervention and referral arrangements made.

15. Baseline Data

The data to be collected at baseline and in subsequent visits are directly related to pre-diabetes or to factors which contribute to diabetes risk (e.g. dietary habits and physical activity).

- Blood test: (non-fasted) measure of glycated haemoglobin, cholesterol and metabolites indicative of dietary intake
- Anthropometry: Measures body weight and size. Being overweight is a risk factor associated with diabetes
- Blood pressure: cardiovascular health is detrimentally affected by poor lifestyle and diabetes risk
- Body composition Provides an analysis of fat mass and percentage body fat
- Urine collection: Allows for the accurate analysis of dietary behaviours
- ActiGraph: Allows for the accurate recording of physical activity

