- Physical Activity Questionnaire: Provides a measure of physical activity levels
- Food frequency questionnaire: Provides a measure of dietary habits
- Health survey: Provides a indication of current perceived health status
- Components of the Personal Diabetes Questionnaire: Provides a indication of an individual's readiness to change their lifestyle behaviours following information regarding their diabetes risk

16. Clinical Study Assessments (Frequency and Duration)

Procedure	Frequency	Duration	Researcher
Venous Blood sample for measure of HbA1c (if surgery does not have a value < 12 months)	1	10 minutes	Performed by a practice nurse or GP at a mid-Wales General Practise
Recording height and weight	3	5 minutes	[name] or other member of the research team. This will take place in the [name] at Aberystwyth University
Recording waist and hip girth	3	5 minutes	[name] or other member of the research team. This will take place in the [name] at Aberystwyth University
Recording blood pressure	3	15 minutes	[name] or other member of the research team. This will take place in the [name] at Aberystwyth University
Venous blood sample	3	10 minutes	[name] or other member of the research team. This will take place in the [name] at Aberystwyth University
Body composition analysis	3	10 minutes	[name] or other member of the research team. This will take place in the [name] at Aberystwyth University
Provision of urine sample for dietary analysis	27	5 minutes	Performed by the participant 3 x per week for 3 weeks after each WARU visit. Samples collected at home.
Actigraph (if randomised to receive)	3	7 days	Performed by the participant. Actigraph worn by the subject around the waist during waking hours. Worn for one week (within each 3 week urine sampling phase) after each

		WARU visit
--	--	------------

17. Qualitative Assessments (Frequency and Duration)

Procedure	Frequency	Duration	Researcher
Providing information prior to gaining informed consent	1	30 minutes	[name] or other member of the research team. This will take place in the [name] at Aberystwyth University

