Administration of the International Physical Activity Questionnaire Short Form	3	10 minutes	[name] or other member of the research team. This will take place in the [name] at Aberystwyth University
Administration of the Food Frequency Questionnaire	2	15 minutes	[name] or other member of the research team. This will take place in the [name] at Aberystwyth University
36-Item Short Form Health Survey Instrument	3	10 minutes	[name] or other member of the research team. This will take place in the [name] at Aberystwyth University
Components of the Personal Diabetes Questionnaire	1	10 minutes	[name] or other member of the research team. This will take place in the [name] at Aberystwyth University
15 minutes pre-diabetes consultation (if randomised to receive)	1	15 minutes	Performed by a practice nurse at a mid-Wales General Practise
End of Study Feedback questionnaire	1	10 minutes	[name] or other member of the research team. This will take place in the [name] at Aberystwyth University

18. Withdrawal Criteria

Participants are free to withdraw from the study at any time without giving prior warning or reason for withdrawal. Participants will not be replaced if withdrawn. Recruitment will continue for the first 6 months of the study. New participants will receive unique individual participant numbers.

19. Storage and Analysis of Clinical Samples

Blood Treatment:

A 1 mL aliquot of whole blood will be transferred from the heparinised vacutainer into a 1.5 mL Eppendorf. The remaining whole blood will be centrifuged at 1500 g for 10 minutes at 4°C. The separated plasma will be pipetted evenly into two separate eppendorfs and frozen at -80°C for subsequent analysis of metabolic content using FIE-MS and GC-MS. Two 1.5 µL aliquots of whole blood will be transferred from the 1.mL aliquot into separate test cartridges and will be analysed for HbA1c and lipid profile by an automated point of care blood analyser (Afinion 2, Abbot, Cheshire, UK).

Urine Treatment:

Urine samples will be centrifuged at 1500 g for 10 minutes at 4°C. 1ml of supernatant will be pipetted evenly into two separate eppendorfs and frozen at -80°C prior to analysis of metabolic content using FIE-MS and GC-MS.

20. End of Trial

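### Nothing in the plan keeps the person who measures waist and hip girth at 3 and 6 months unaware of the arm, though the division of roles would largely allow it

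*Combined protocol and SAP*

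**What the plan says.** All references are to the combined protocol and SAP.

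- **Who measures.** The section 16 table has a row for "Recording waist and hip girth", done at three visits at the university by a named researcher "or other member of the research team". Height and weight, blood pressure, blood sampling and body composition carry the same entry.
- **Who allocates.** Section 14: "Randomisation will be conducted primarily by the academic supervisor". Section 13 places allocation after the baseline visit.
- **Who is told.** Section 14: "Church surgery will be informed of the patients who have been randomised to receive the intervention and referral arrangements made". It does not say whether the university measurers are told or kept unaware.
- **Who delivers.** The section 17 entry for the consultation reads "Performed by a practice nurse at a mid-Wales General Practise".
- **Comparator.** Section 5 says that the study will "assess the effectiveness of a 15 minute one to one consultation compared to no treatment", so participants know which arm they are in.
- **Use of the readings.** Girth is a secondary measure at 3 and 6 months (section 4). Section 21 applies a two-factor mixed ANOVA to all physiological measures, with significance at P < 0.05.

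No section mentions blinding or masking of anyone.

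**The concern.** Girth depends on how the measurer places and reads the instrument. Section 13 names the instrument but gives no number of readings per visit and no duplicate reading. A measurer who knows the arm and expects benefit can shift readings without meaning to.

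Expectation of benefit is plausible here. Section 2 reports that the earlier uncontrolled consultation was followed by significant falls in BMI, waist circumference and HbA1c, and section 13 attributes that study to the present team.

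At stake is the girth comparison between arms. A shift that differs by arm is indistinguishable from a treatment effect in the planned ANOVA, and no analysis can remove it afterwards.

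**Working it through.** The plan gives no power, effect size or SD, so there is no figure of its own to reproduce. The check has two parts.

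**1. Could the follow-up measurer know the arm, and which readings are exposed?**

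- Section 16 admits any team member, section 14 leaves allocation partly open, and nothing excludes an allocator from measuring.
- Other routes exist. Participants know their arm and are not asked to keep it to themselves. The chief investigator handles communication with participants (section 24). The ActiGraph subgroup is five from each arm (section 13), so whoever selects it needs the allocation.
- One route is already closed. The acceptability questionnaire, which asks about the consultation, comes at the end of the 6-month visit (section 13).
- Allocation follows baseline, so 2 of the 3 girth readings per participant (3 and 6 months) are exposed.
- Blood pressure is recorded with a named device after 10 minutes of quiet sitting (section 13), and HbA1c by an automated analyser (section 19). Both leave less room for the observer.
- The primary quantities in section 4 are the number in the HbA1c range, the percentage consenting and the percentage completing each visit. None uses a girth reading.

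**2. How much could a differential bias matter? (illustration)**

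Inputs: 40 participants (section 23), half without the intervention (section 3), so n = 20 per arm; alpha 0.05 (section 21), taken as two-sided; no true effect. The bias b, in SD units, is an assumption.

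For a two-group comparison the shift in the test statistic is δ = b / √(2/n), with √(2/20) = 0.316.

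- b = 0.2: δ = 0.2/0.316 = 0.63
- b = 0.3: δ = 0.3/0.316 = 0.95

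Normal formula: false-positive rate = 1 − Φ(1.96 − δ) + Φ(−1.96 − δ). The last column uses the noncentral t distribution with 2n − 2 degrees of freedom.

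| n per arm | b (SD) | Normal | Noncentral t |
|---|---|---|---|
| 20 | 0 | 5% | 5% |
| 20 | 0.1 | 6.2% | 6.1% |
| 20 | 0.2 | 9.7% | 9.5% |
| 20 | 0.3 | 15.8% | 15.2% |
| 20 | 0.5 | 35.3% | 33.8% |
| 16 (assumed 20% loss) | 0.2 | 8.7% | 8.5% |
| 16 (assumed 20% loss) | 0.3 | 13.6% | 13.0% |

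If the SD of waist were 10 to 14 cm (an assumption), 0.2 to 0.3 SD would be a sustained shift between arms of 0.2 × 10 = 2 cm to 0.3 × 14 = 4.2 cm.

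These are not this trial's error rates. The planned test is a mixed ANOVA over three visits, followed by Bonferroni-corrected t-tests. Its behaviour depends on the within-person correlation, which is not given. A high correlation would make the same shift in centimetres count for more, and the Bonferroni step would make it count for less.

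**The case against.** The strongest case against is that this reads silence as practice. No section says that measurers are told the arm; only the surgery is. The name of the default measurer has been removed from the public text, so the documents cannot show that the measurer and the allocator are the same person. The outcome is secondary in a feasibility study, and the size of the bias is assumed.

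Much of this stands, and it rules out several stronger readings that a reader might infer:

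- **That readings will be taken with knowledge of the arm.** The documents show only that nothing prevents it.
- **That blood pressure is equally exposed.** A device reads it after a set rest, so the argument rests on girth.
- **That the bias will carry into the main trial's effect estimate.** The study is meant to inform a later trial, but no section says that girth estimates will size or justify it. The future trial's stated target is blood glucose control.
- **That the false-positive rate is 9-15%.** That range holds only for the assumed bias and a simple t-test.
- **That blinding is free.** The supervisor is not the only possible allocator, the chief investigator is the participants' contact, and visits of about 120 to 150 minutes give unblinded participants time to mention their arm.

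What the objection does not remove is the gap itself. A measurer-dependent outcome is to be tested between arms, and someone who follows the plan to the letter may measure it knowing the arm.

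**Conclusion.** The concern holds in a limited form. The plan has no safeguard to keep the 3- and 6-month girth measurer unaware of allocation: any team member may measure, and an allocator is not excluded. Baseline girth is not exposed, blood pressure is less open to observer bias, and the primary feasibility counts are unaffected.

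The size cannot be derived from the documents. The illustration indicates only that a modest differential shift would matter for a test with about 20 per arm. It rests on 40 participants split equally, a two-sided 5% test and an assumed bias.

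This is a minor point. It is worth making because delivery already sits with the surgery, allocation sits mainly with the supervisor, and measurement takes place at the university unit.

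**What to change.** Add to sections 14 and 16 that:

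- allocation is held by the supervisor and the surgery;
- girth at 3 and 6 months is measured by an existing team member who did not allocate and is not told the arm. For simplicity, the same person takes the other physical measurements at that visit;
- participants are asked not to disclose their arm until that visit's measurements are finished;
- any unblinding of the measurer is logged and reported.

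Keep the acceptability questionnaire at the end of the 6-month visit, where section 13 already puts it. If blinded measurement proves unworkable, report its absence as a limitation of the girth results.

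The cost is a few sentences and some care with rostering, with no extra staff. Arm-related contact with participants, including handling of the ActiGraph subgroup, may have to move away from the measurer. In a small team with unblinded participants some accidental unblinding should be expected. The log would show how often it happens, which is useful feasibility information for a later trial.

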Further information regarding the study can be sought via telephone, email or visiting the university research facility in person. Any questions the participant may have can be asked at any point prior to giving consent using any of these methods. Patients are free to withhold consent without giving reason. In accordance with the Welsh Language Act 1993, all correspondence will be translated into Welsh. For patients confirming their involvement, verbal and written informed consent will be sought in person at the start of their first visit to the Well-being Assessment Research Unit (WARU) before being inducted into the study (> 24 hours between receipt of the

study invite letter & participant information sheet and signing informed consent). Those who decline involvement will receive usual care from their GP.

13. Study Procedures

Participants will be required to visit the WARU ([name]) on 3 separate occasions, for baseline, 3 month and 6 month testing. During the baseline visit, the procedures and protocol of the study will be explained and informed consent will be received. Participant's height (Holtain Ltd, Crymych, UK) and body mass (wearing loose fitting clothing; Seca 899, Hamburg, Germany) will be collected to calculate body mass index (BMI) and waist and hip girth recorded (Seca 201, Seca GmbH & Co, Hamburg, Germany). Next, participants will be asked to sit quietly for 10 minutes in the laboratory before blood pressure is recorded from the upper non-dominant arm (Omron M3, Omron Healthcare Ltd, Milton Keynes, UK). Participants will remain seated prior to a 6 mL blood sample being obtained from the antecubital vein and collected into a heparinised vacutainer (BD Vacutainer Systems, Plymouth, UK), with minimal stasis, using standard venepuncture methods performed by a trained member of the research team. Should patients HbA1c be outside the required values during the baseline visit, they will be informed and will take no further part in the research. WARU will inform the participant's GP if their HbA1c is indicative of diabetes. Body composition will be analysed using bioelectrical impedance (Bodystat 1500, Bodystat Ltd, Douglas, British Isles).

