and the second half provided patients with lifestyle advice on preventing diabetes. The consultation to be used in the proposed study does not require general practise to collect baseline data and therefore the consultation time has been reduced from 30 minute to 15 minutes. The consultation will provide the participant with one to one information regarding the benefits of physical activity and healthy eating. Emphasis will be placed on the importance of achieving at least 150 minutes of moderate physical activity each week as well as adhering to healthy dietary habits, based on the NHS Eatwell Guide (Eatwell Guide, 2016). Furthermore, participants will have the opportunity to discuss prediabetes with a trained practice nurse and ask any questions they may have. Participants placed in CON will not receive the consultation and will only attend visits to the WARU. Due to logistical and financial implications, a subgroup of participants will also be randomised for additional physical activity monitoring. 5 participants from INT and 5 from CON will receive an Actigraph (see below for further information on the Actigraph).

Dietary Monitoring:

Metabolic fingerprinting and metabolic profiling of human urine is able to provide a comprehensive and quantitative snapshot of dietary exposure for 12 – 24 hrs prior to urine collection. While a single sample snapshot is not representative of an individuals' habitual dietary exposure, a series of snapshots over a prolonged time period can give a robust overview of an individual's nutritional health. Previous work by IBERS has demonstrated a community based urine collection protocol ($n = 16$) as a successful and non-disruptive method for monitoring habitual diet. Participants will be provided with a urine collection kit consisting of; of 14 cm non-sterile urine collection straws 4 mL additive free evacuated vacutainer tubes and a 125 mL collection container. Once urine has been collected, the sealed vacutainer tubes will be stored in an absorbent pouch within a sealed leak-proof bag and kept in the refrigerator. All urine storage equipment and instructions are fully compliant with the UN3373 standard for Category B

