The testing stage of this study will be defined as finished when the last participant completes the final visit (6 month testing). Additionally, the research will be stopped if there is a lack of

recruitment after 6 months or if a clinical or research incident prompts a review.

21. Statistics and Data Analysis

A computerized statistical package will be used to analyse all data associated with the primary and secondary outcomes (SPSS version 17.0, SPSS inc., Chicago, IL). Normally distributed data will be presented as mean \pm SD. Scores from the questionnaires will be calculated based upon their respective scoring protocols. A two factor mixed model ANOVA will be conducted on all physiological measures and questionnaire responses to determine any differences between groups over time. Significant differences identified by the ANOVA will be further analysed by post hoc independent or paired t-tests with Bonferroni correction. Data mining of urine samples using methods such as PCA will be employed to determine if foods can be discriminated. Statistical significance will be accepted at $P < 0.05$.

22. Sample Size Calculation

The sample size was decided based upon potential numbers of eligible patients provided to the research team by the participating general practice. Potential numbers are based upon the amount of registered patients with a $\text{BMI} > 25 \text{ kg/m}^2$ or an existing $\text{HbA1c} < 12$ months. As this is a feasibility study for a future large scale randomised control trial, no formal sample size calculation has been employed.

23. Planned Recruitment Rate

Previous work completed by the research team demonstrated an approximate 50% uptake in consultation offers in patients with pre-diabetes ($n = 420$). Our partnering surgery currently have 737 patients with a $\text{BMI} > 25 \text{ kg/m}^2$. A further 216 patients have an HbA1c (recorded within the last year) within the eligible range. Furthermore, Church surgery identifies approximately 6 new

‘at risk’ individuals each week. Therefore, we estimate it will take one month to recruit 40 patients into the study.

24. Data Management

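### Section 21 specifies no between-arm difference with a confidence interval at 3 or 6 months for the secondary outcomes, and states no baseline adjustment for the comparison at a visit

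*Combined protocol and SAP*

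**What the plan says.** Section 4 frames the secondary aim as a question about the consultation at two fixed times: "Secondary research questions aim to determine the impact of the consultation on the following measures at 3 and 6 months". The list that follows covers HbA1c, cholesterol, BMI, girths, blood pressure, body composition, physical activity and diet.

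The analysis of these outcomes is set out only in section 21. The main step is: "A two factor mixed model ANOVA will be conducted on all physiological measures and questionnaire responses to determine any differences between groups over time". The second step depends on the first: "Significant differences identified by the ANOVA will be further analysed by post hoc independent or paired t-tests with Bonferroni correction". For presentation, "Normally distributed data will be presented as mean" and SD. The section names no covariate, between-arm estimate or confidence interval. It does not say whether the t-tests use raw values or changes from baseline, or which ANOVA effect (group, time or their interaction) opens them.

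Other sections bear on the point:
- Section 13 schedules the measurements at baseline, 3 and 6 months, so baseline values will exist. The exception is "Food Frequency Questionnaire (FFQ; EPIC-Norfolk; baseline and 6 months".
- Section 13 holds baseline HbA1c to the entry range: "Should patients HbA1c be outside the required values during the baseline visit, they will be informed and will take no further part".
- Section 13 limits activity monitors to a subgroup: "5 participants from INT and 5 from CON will receive an Actigraph".
- Section 14 describes minimisation: "remaining participants will be randomly allocated into either the intervention or control based upon age", with sex and a BMI threshold of 30 also used.
- Section 22 says there is no formal sample size. Section 23 expects 40 recruits in a month, and section 18 lets recruitment run for six months.

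**The concern.** The group-by-time interaction asks whether the arms' profiles differ anywhere across three visits. It does not say by how much they differ at 3 or at 6 months. The only planned comparison that can do so is the independent t-test, and that is reached only after a significant ANOVA. If the ANOVA is not significant, the plan specifies no between-arm estimate at all. Yet a feasibility study meant to inform a larger trial has most use for an estimate and its uncertainty. A reader could work out an unadjusted difference from the reported means and SDs, but not a baseline-adjusted one.

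A second, smaller matter is the paired t-tests. They are within-arm comparisons. If a time effect shared by both arms could open them, one arm may reach significance and the other not, by chance, and this can be misread as an effect of the consultation.

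**Working it through.** The plan gives no power, SD or interval figure for these outcomes, so there is nothing of its own to reproduce.

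**Inputs.** From the documents: 40 recruits (section 23), half without the intervention (section 3), so n = 20 per arm; significance level 0.05 (section 21), taken as two-sided. Assumed: SD 1, the same at each visit; baseline to follow-up correlation r = 0.3, 0.5, 0.7 or 0.8; no dropout. Because recruitment may run for six months, n = 40 per arm is also shown.

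**Formulas for the 95% half-width at one visit.**
- Raw values: t(2n−2) × √(2/n).
- Change scores: the same × √(2(1−r)).
- Baseline-adjusted (ANCOVA): t(2n−3) × √(2/n) × √(1−r²) × √(1+1/(2n−4)). The last factor allows for chance baseline imbalance.

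**Numbers in, n = 20.** Raw: 2.024 × 0.3162 = 0.64. Change scores at r = 0.7: 0.640 × √0.6 = 0.50. Adjusted at r = 0.7: 2.026 × 0.3162 × 0.714 × 1.014 = 0.46.

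| Half-width (SD units) | r = 0.3 | r = 0.5 | r = 0.7 | r = 0.8 |
|---|---|---|---|---|
| 20 per arm, raw | 0.64 | 0.64 | 0.64 | 0.64 |
| 20 per arm, change scores | 0.76 | 0.64 | 0.50 | 0.40 |
| 20 per arm, adjusted | 0.62 | 0.56 | 0.46 | 0.39 |
| 40 per arm, raw | 0.45 | 0.45 | 0.45 | 0.45 |
| 40 per arm, adjusted | 0.43 | 0.39 | 0.32 | 0.27 |

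If r were zero, adjustment at 20 per arm would give 2.026 × 0.3162 × 1.014 = 0.65 against 0.64 raw, so the possible loss is negligible.

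**HbA1c.** Restricting the baseline range lowers r. If restriction cuts the baseline SD to a fraction u, r becomes r·u/√(1−r²+r²u²). Starting from an assumed r = 0.8:
- u = 0.5 gives 0.4/√0.52 = 0.55.
- u = 0.25 gives 0.2/√0.40 = 0.32.

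The factor √(1−r²) is then about 0.83 or 0.95, so the narrowing is between modest and slight.

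**How often the gate stays shut.** In a simulation with 20 per arm, equal correlation between visits and an assumed 0.5 SD effect at both follow-ups (4,000 trials per setting), the interaction test was significant in 35%, 54% and 72% of trials at r = 0.5, 0.7 and 0.8. If only the interaction opens the t-tests, the remaining 65%, 46% and 28% would have no planned visit comparison.

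**Paired tests.** Simulated with 20 per arm, both arms changing equally by 0.3 or 0.5 SD, r = 0.5, 0.7 or 0.9, and Bonferroni over 2 or 6 tests. The event is at least one significant change from baseline in the intervention arm and none in control.
- A time effect opens the tests: roughly 10 to 24% of trials in most scenarios (1% or less at r = 0.9 with a 0.5 SD change).
- Only the interaction opens them: about 2% or less.

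**ActiGraph.** With 5 per arm the unadjusted half-width is t(8) × √(2/5) = 2.306 × 0.632 = 1.46 SD, too wide for inference.

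**The case against.** The strongest reply is that the main test is sound. The interaction includes baseline as a time level, so it tests differential change, and its power is close to that of a baseline-adjusted comparison when correlation is high. At 6 months in the same simulation, the adjusted comparison had 42%, 58% and 72% at r = 0.5, 0.7 and 0.8, against 35%, 54% and 72% for the interaction. This stands: power is not the argument, and a reader who inferred that the planned analysis is invalid or ignores baseline would be wrong.

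Second, the t-tests might be run on change scores. Section 21 does not exclude this. A reader might infer that adjustment cuts the half-width from 0.64 to 0.39 SD. That holds only if raw values are compared and r is 0.8. Against change scores at r = 0.8 the gain is 0.40 to 0.39.

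Third, the wording about group differences over time most naturally points to the interaction as the gate. On that reading the misleading within-arm pattern is rare. A reader might infer that the plan will treat within-arm significance as evidence of effect. The text does not say so; it merely leaves a common time effect unexcluded.

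Fourth, this is a feasibility study with no formal sample size, and the outcomes are secondary. That limits the severity. It does not remove the question section 4 asks, and an estimate with its interval suits a feasibility study better than gated significance tests.

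**Conclusion.** The point holds as a minor one. The plan asks for impact at 3 and 6 months but specifies no between-arm difference with a confidence interval at either visit. The only comparison that can refer to a single visit is conditional on a significant ANOVA and carries no stated baseline adjustment. That part rests on the text alone.

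The size of the precision gain rests on assumed SDs and correlations. Adjustment is never materially worse than either reading of the t-test. It is clearly better than raw values from about r = 0.5 upwards, and better than change scores mainly at lower r. It may add little for HbA1c, although the missing estimate and interval matter there whatever the correlation. The ambiguity over the paired tests deserves one clarifying sentence but would not carry the point by itself. Nothing here affects the primary feasibility counts.

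**What to change.** Reword section 21 as follows.

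- For each continuous secondary outcome, report the between-arm difference at 3 and 6 months (food frequency questionnaire at 6 months only) with a 95% confidence interval, whatever the ANOVA result.
- Adjust for the baseline value of the outcome and preferably for the minimisation factors (age 60+, sex, BMI 30+). The BMI factor may be left out when BMI is the outcome.
- ANCOVA at each visit or a mixed model would both serve. Name a transformation or other suitable method for clearly non-normal outcomes.
- Either state that the intervals are for estimation, or keep Bonferroni over the two visits (0.05/2 = 0.025 each).
- Say which ANOVA effect opens the post hoc tests, and that within-arm paired tests are not evidence of an effect of the consultation.
- Leave the urine PCA exploratory and report the ActiGraph data descriptively.

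The cost is the rewording and up to four model degrees of freedom (baseline plus three factors). No extra visits or data are needed. Where r is about 0.3, the precision gain is small (0.64 to 0.62 SD at 20 per arm). The change should be made before outcome data are seen by arm.
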